At tolerated doses (MTD = 2 mg QD and 5 mg QOD), pomalidomide has been shown to be active in subjects with relapsed or refractory MM (study CC-4047-00-01). In 45 subjects who received doses of pomalidomide ranging, by cohort, up to 10 mg daily, the most commonly occurring dose-limiting toxicity (DLT) was reversible neutropenia. As with other IMiDs administered to subjects receiving concomitant systemic steroids, deep vein thrombosis (DVT) was seen. Pivotal phase 2 and 3 studies of pomalidomide/ dexamethasone in relapsed/refractory MM yielded ORRs of 33% and 31%, respectively. In a randomized phase 2 study, pomalidomide with/without low-dose dexamethasone in patients with relapsed/refractory multiple myeloma was assessed. Patients who had received  $\geq 2$  prior therapies including lenalidomide and bortezomib were randomized to POM (4 mg/day on days 1-21 of each 28-day cycle) with/without dexamethasone (40 mg/week). In the pomalidomide/ dexamethasone arm, median PFS was 4.2 months, ORR was 33%, CR 3%, median response duration was 8.3 and median overall survival 16.5. Grade 3-4 neutropenia occurred in 41%; no grade 3-4 peripheral neuropathy was reported. In a phase 3 study (5 median prior lines, 100% lenalidomide/ bortezomib exposed, 95% lenalidomide refractory and 75% double-refractory), ORR 31%,  $\geq$ VGPR 6% and  $\geq$ CR 1%. At a median f/u of 10 mos, median PFS 4 mos and median OS 12.7 mos. The most common grade 3-4 haematological adverse events in the pomalidomide plus low-dose dexamethasone was neutropenia 48%, anaemia 33%, and thrombocytopenia 22%. Grade 3-4 non-haematological adverse events in the pomalidomide plus low-dose dexamethasone included pneumonia 13%, bone pain 7%, and fatigue 5%. There were 4% treatment-related adverse events leading to death in the pomalidomide plus low-dose dexamethasone group.

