In the relapsed/refractory setting, a Phase 2 study of Biaxin®, pomalidomide, and dexamethasone (ClAPd) was studied in 120 patients with median of 5 prior lines (84% lenalidomide refractory). An ORR of 60% with ≥VGPR 23%, median PFS and DoR 7.7 and 9.3 mos, respectively and median OS 19.3 mos was seen. No influence on PFS was seen with lenalidomide or lenalidomide/bortezomib refractoriness nor significant differences in PFS/OS between low and high-risk patients. The most common gr 3/4 AEs were neutropenia 47% (gr 4 14%), lymphopenia 37% (gr 4 6%) and thrombocytopenia 33% (gr 4 16%) with no grade 5 events and a discontinuation rate of 3%.

This study is intended to investigate the combination of daratumumab, clarithromycin (Biaxin®), pomalidomide and dexamethasone [D-ClAPd] in multiple myeloma patients who have relapsed or refractory MM and have been previously exposed to daratumumab. Primary

endpoint will be response rate to treatment. Secondary endpoints will include toxicity of the combination, time to maximum response, and time to disease progression.

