#### *1.3.2.1 Daratumumab IV Monotherapy Studies*

Among the 156 patients treated with a therapeutic dose of daratumumab 16 mg/kg administered intravenously as monotherapy in Studies GEN501, MMY2002, and MMY1002:

- 6 patients (4%) discontinued daratumumab treatment due to a treatment emergent adverse event (TEAE), none of which were considered by the investigator to be related to daratumumab.
- 3 patients (2%) died due to TEAEs within 30 days after the last dose of study drug.
- The most frequently reported TEAEs were fatigue (40%); nausea and anemia (28% each); back pain (26%); cough (24%), neutropenia (23%); pyrexia (22%), upper respiratory tract infection (22% each), and thrombocytopenia (21%).
- SAEs were reported in 33% of patients, the most frequently reported SAEs were pneumonia (6%) and pyrexia, hypercalcemia, and general physical health deterioration (3% each).
- Grade 3 or 4 TEAEs were reported in 56% of patients; most commonly these were anemia (17%), thrombocytopenia (14%), neutropenia (12%), lymphopenia (6%), leukopenia, pneumonia, and hypertension (5% each).

TEAEs of infection were reported in 59% of patients. The most frequently reported were upper respiratory tract infection (22%), nasopharyngitis (15%), pneumonia (9%), sinusitis (7%), and urinary tract infection (6%). Grade 3 and 4 TEAEs of infections or infestations were reported in 10% and 1% of patients, respectively.

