## 4.2 Number of Patients

Approximately 40 patients will be enrolled and treated on study.

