### 8.1.5 Safety Analysis

Safety parameters will include SAEs, TEAEs, physical examination findings (including ECOG performance status), vital sign measurements, standard clinical laboratory parameters (serum chemistry, hematology, urinalysis), and ECG parameters. Adverse events will be graded according to the NCI-CTCAE v4. The incidence of DLTs will also be evaluated.

Safety analyses in general will be descriptive and will be presented in tabular format with the appropriate summary statistics.

A TEAE is defined as an adverse event that emerges during the treatment period (from first dose date till 30 ( $\pm$  5) days after the last dosing date), having been absent at pre-treatment; or reemerges during treatment, having been present at baseline but stopped prior to treatment; or worsens in severity after starting treatment relative to the pre-treatment state, when the adverse event is continuous. The number and percentage of patients reporting TEAEs will be tabulated by the worst NCI-CTCAE grade, system organ class (SOC), and preferred term.

Similarly, the number and percentage of patients reporting treatment-emergent SAEs will be tabulated, as well as TEAEs/SAEs considered related to Daratumumab, Clarithromycin, Pomalidomide, and Dexamethasone.

A by-patient AE (including TEAE) data listing will be provided including, but not limited to, verbatim term, preferred term, SOC, NCI-CTCAE grade, and relationship to study drug.

Deaths, other SAEs, and other significant adverse events, including those leading to permanent discontinuation from Daratumumab, Pomalidomide, and Dexamethasone, will be listed.

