#### 8.1.7 Futility Analysis and Stopping Rules

If  $>4$  deaths have been observed, regardless of how many patients have been enrolled at that point or by that time, the study will be stopped due to futility.

If Grade 3-4 infection rate >15% is seen, protocol enrollment will be put on hold and amendments for risk reduction will be implemented.

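### The Grade 3-4 infection hold in Section 8.1.7 leaves fatal infections out of its count and gives no denominator, minimum number of patients or evaluation times (SHOULD-FIX)

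*Combined protocol and SAP*

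**What the plan says.** Section 8.1.7 holds two rules. One stops the study for futility once more than 4 "deaths have been observed, regardless of how many patients have been enrolled at that point or by that time". The other is the infection rule: "If Grade 3-4 infection rate >15% is seen, protocol enrollment will be put on hold", after which "amendments for risk reduction will be implemented". The death rule says how it relates to the number enrolled; the infection rule does not. No other section supplies a denominator, a minimum number, a time window or a look schedule for it. Section 10 sets DSMC review every 6 months and does not mention the 15% limit.

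On grading, Section 8.1.5 says "Adverse events will be graded according to the NCI-CTCAE v4" and tabulates treatment-emergent events by worst grade. Section 1.1 treats Grade 5 as a category apart from Grade 3/4 when it describes the earlier trial of clarithromycin, pomalidomide and dexamethasone: "with no grade 5 events and a discontinuation rate of 3" per cent. The list of events of special interest in Section 9.2.1.2, by contrast, uses an open-ended grade for infections (Grade 4 and above).

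The planned size is in Section 4.2: "Approximately 40 patients will be enrolled and treated on study".

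**The concern.** This is the only enrolment hold in the plan that is specific to infection, and it has two gaps.

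First, the most serious infections do not move it. A patient whose infection reaches Grade 5 is, by worst grade, not a Grade 3-4 case. A trial with several infectious deaths could show a lower hold rate than one where the same patients survived.

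Second, an observed percentage is compared with 15% without saying which patients form the denominator, when the comparison starts or how often it is made. Two teams applying the sentence to the same data could reach opposite decisions. At very small numbers a single event is enough. At stake are a hold and compulsory amendments set off by chance on one side, and a missed signal on the other.

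**Working it through.** **Inputs.** Limit: observed rate strictly above 15% (Section 8.1.7). Death rule: more than 4 deaths (same section). Maximum n: 40 (Section 4.2). The plan gives no operating figure for the infection rule. As a check on method, the efficacy rule in Section 8.1.1 (8 or more of 40, 9% against 25%) does reproduce by exact binomial: P(X ≥ 8) = 0.024 at 9% and 0.818 at 25%, within the stated 5% and 80%.

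**True infection rates are assumed.** The documents report none for this four-drug regimen. Two figures from other regimens suggest a range:
- Daratumumab monotherapy (Section 1.3.2.1): "Grade 3 and 4 TEAEs of infections or infestations were reported in 10% and 1% of patients, respectively", so about 11%.
- Pomalidomide/dexamethasone, phase 3 (Section 1.1): Grade 3-4 events included "pneumonia 13%, bone pain 7%, and fatigue 5" per cent, so 13% for pneumonia alone.

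I use 10% and 13% as background-like rates, and 20% and 30% as excess rates.

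**Step 1: fatal infections.** Take 40 patients, 6 with a Grade 3-4 infection and 4 others with a fatal infection, and no other deaths.
- Infection rule: 6/40 = 15.0%, not above 15%. No hold.
- Death rule: 4 deaths, not more than 4. No stop.
- Patients with a Grade 3 or higher infection: (6 + 4)/40 = 25%.

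This can happen even if the rate is checked after every patient. With Grade 3-4 events in patients 7, 14, 20, 27, 34 and 40, the running rate at each event is 1/7 = 14.3%, 2/14 = 14.3%, 3/20 = 15.0%, 4/27 = 14.8%, 5/34 = 14.7% and 6/40 = 15.0%. It never exceeds 15%.

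**Step 2: smallest count that exceeds 15%.** This is the smallest whole x with x/n > 0.15.

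| Patients (n) | Events needed |
|---|---|
| 1-6 | 1 |
| 7-13 | 2 |
| 14-19 | 3 |
| 20-26 | 4 |
| 27-33 | 5 |
| 34-39 | 6 |
| 40 | 7 |

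One event suffices up to patient 6 (1/6 = 16.7%, and higher with fewer patients), but not from patient 7 (1/7 = 14.3%). The chance of at least one event in the first 6 is 1 − (1 − p)^6: 1 − 0.90^6 = 47% at 10%, and 1 − 0.87^6 = 57% at 13%.

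**Step 3: chance of a hold by patient 40.** Assume one yes/no infection status per patient, independent, with rate p, known in order of entry. Carry the distribution of the event count forward one patient at a time, P(n, x) = P(n−1, x)(1 − p) + P(n−1, x−1)p. At each look, remove and add up the probability at counts above 0.15n. With looks at 10, 20, 30 and 40, the triggering counts are 2, 4, 5 and 7. A single look at 40 is P(X ≥ 7).

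| True rate | One look at 40 | Looks at 10/20/30/40 | After each patient | After each patient from the 10th |
|---|---|---|---|---|
| 10% | 10% | 35% | 61% | 49% |
| 13% | 26% | 53% | 76% | 67% |
| 20% | 71% | 86% | 95% | 92% |
| 30% | 98% | 99% | 99.7% | 99.6% |

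At the same true rate of 10%, the unstated look schedule alone moves the chance of a hold from 10% to 61%.

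**The case against.** The best defence is that the rule is meant to be cautious. It pauses enrolment and does not end the trial. For a four-drug regimen, a sensitive trigger is a fair choice, and a false hold costs time without touching the primary analysis. That stands, and it is why this is not a must-fix. It does not explain leaving out fatal infections, nor does it tell the team when to apply the rule.

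Three stronger readings are tempting, and the documents do not support them.

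- **That a fatal infection counts nowhere.** It counts toward the more-than-4-deaths rule, every death must be reported as an SAE (Section 9.1.2), and the DSMC reviews AEs and SAEs and may recommend stopping. The gap is in the infection numerator only. It remains a gap because the death rule needs a fifth death.
- **That the hold will probably fire at the rate the plan expects.** The plan states no expected infection rate for this combination, and whether a hold is more likely than not depends on the schedule. The after-each-patient column also assumes each outcome is known before the next patient enters. Infections build up over months while enrolment continues. A simulation counting enrolled patients and holds during accrual only (assumed 1, 2 or 4 patients a month, events spread evenly over 5 to 8 months, none of it from the documents) gave 12% to 53% at a true 10% and 20% to 68% at 13%. The 61% and 76% are therefore upper-end values.
- **That 15% contradicts the 13% pneumonia figure.** A limit set above one background figure from another regimen is not an inconsistency. How far above background to set it is the sponsor's judgement.

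An investigator might also count a fatal infection through its earlier Grade 3 or 4 stage. The text does not say so, and tabulation by worst grade points the other way.

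**Conclusion.** The point holds as a SHOULD-FIX. On the wording, fatal infections are outside the count that triggers the hold, and 6 Grade 3-4 plus 4 fatal infections in 40 patients (25% affected) would trip neither rule in Section 8.1.7. That is a constructed case showing what the text allows, not an estimate of how often it would occur.

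The missing denominator, minimum number and evaluation times also hold on the text. A single event halts enrolment if it is counted among 6 or fewer patients. Beyond that, the rule has no definite error rate: 10% to 61% at an assumed true rate of 10%, and 26% to 76% at 13%, depending on a schedule the plan does not give. These figures rest on independent outcomes known in order of entry and on rates borrowed from other regimens.

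**What to change.** Amend the second rule in Section 8.1.7 as follows.

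1. Replace the Grade 3-4 range with Grade 3 or higher, including fatal, counted once per treated patient.
2. State the denominator, the minimum number of treated patients before the rule applies, and the evaluation times.
3. Report the probability of a hold over a range of true rates for the rule chosen. The rates should now refer to Grade 3 or higher infection.

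As an illustration, keep the observed limit of more than 15%, start at 10 treated patients and check after each one. The chance of a hold is then 49% at a true 10%, 67% at 13%, 92% at 20% and 99.6% at 30%. Compared with no minimum, this lowers the chance at 10% from 61% to 49% and costs little at 20% (95% to 92%) or 30% (99.7% to 99.6%).

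The cost is a one-paragraph amendment. The downside is that nothing triggers automatically before the minimum number. Grade 3 or higher infections before then should go to ad hoc DSMC review, which Section 10 already permits by allowing additional meetings. The numerical limit, and whether to use a boundary that demands stronger evidence at the price of lower sensitivity, remain the sponsor's choice.

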## 9. ADVERSE EVENTS

### 9.1 Overview

As the sponsor of the Study, PRINCIPAL INVESTIGATOR shall be solely responsible for complying, within the required timelines, any safety reporting obligation to competent Health Authorities, IRB/ECs and any participating (co or sub) investigators, as defined in applicable laws and regulations. For the purposes of this section, safety data includes adverse events, product quality complaints (PQCs), and special situations including pregnancies.

The PRINCIPAL INVESTIGATOR will provide safety information to Janssen Scientific Affairs, LLC on adverse events, special situations including pregnancies and product quality complaints as defined within this section

#### 9.1.1 Adverse Event Definition

Adverse event (AE) means any untoward medical occurrence in a patient or patient administered a pharmaceutical product; the untoward medical occurrence does not necessarily have a causal relationship with this treatment. An AE can therefore be any unfavorable and unintended sign (including an abnormal laboratory finding), symptom, or disease temporally associated with the use of a medicinal (investigational) product whether or not it is related to the medicinal product. This includes any newly occurring event, or a previous condition that has increased in severity or frequency since the administration of study drug.

An abnormal laboratory value will not be assessed as an AE unless that value leads to discontinuation or delay in treatment, dose modification, therapeutic intervention, or is considered by the investigator to be a clinically significant change from baseline.

The investigator (or physician designee) is responsible for verifying and providing source documentation for all adverse events and assigning the attribution for all adverse events for patients enrolled.

#### 9.1.2 Serious Adverse Event Definition

Serious AE (SAE) means any untoward medical occurrence at any dose:

- Results in death.
- Is life-threatening (refers to an AE in which the patient was at risk of death at the time of the event. It does not refer to an event which hypothetically might have caused death if it were more severe).
- Requires inpatient hospitalization or prolongation of an existing hospitalization (see clarification in the paragraph below on planned hospitalizations).

- Results in persistent or significant disability or incapacity. (Disability is defined as a substantial disruption of a person's ability to conduct normal life functions).
- Is a congenital anomaly/birth defect.
- Is a medically important event. This refers to an AE that may not result in death, be immediately life threatening, or require hospitalization, but may be considered serious when, based on appropriate medical judgment, may jeopardize the patient, require medical or surgical intervention to prevent 1 of the outcomes listed above, or involves suspected transmission via a medicinal product of an infectious agent. Examples of such medical events include allergic bronchospasm requiring intensive treatment in an emergency room or at home, blood dyscrasias or convulsions that do not result in inpatient hospitalization, or the development of drug dependency or drug abuse; any organism, virus, or infectious particle (eg, prion protein transmitting Transmissible Spongiform Encephalopathy), pathogenic or nonpathogenic, is considered an infectious agent.

Clarification should be made between a serious AE (SAE) and an AE that is considered severe in intensity (Grade 3 or 4), because the terms serious and severe are NOT synonymous. The general term severe is often used to describe the intensity (severity) of a specific event; the event itself, however, may be of relatively minor medical significance (such as a Grade 3 headache). This is NOT the same as serious, which is based on patient/event outcome or action criteria described above and is usually associated with events that pose a threat to a patient's life or ability to function. A severe AE (Grade 3 or 4) does not necessarily need to be considered serious. For example, a white blood cell count of  $1000/\text{mm}^3$  to less than 2000 is considered Grade 3 (severe) but may not be considered serious. Seriousness (not intensity) serves as a guide for defining regulatory reporting obligations.

**NOTE: DEATH FOR ANY REASON SHOULD BE REPORTED AS A SERIOUS ADVERSE EVENT.**

### Hospitalization

For reports of hospitalization, it is the sign, symptom or diagnosis which led to the hospitalization that is the serious event for which details must be provided.

Any event requiring hospitalization or prolongation of hospitalization that occurs during the study must be reported as a serious adverse event, except hospitalizations for the following:

- Hospitalizations not intended to treat an acute illness or adverse event (e.g., social reasons such as pending placement in long-term care facility)
- Surgery or procedure planned before entry into the study. [Note: Hospitalizations that were planned before the start of data collection and where the underlying condition for which the hospitalization was planned has not worsened will not be considered serious adverse events. Any adverse event that results in a prolongation of the originally planned hospitalization is to be reported as a new serious adverse event.]
- Hospitalizations for close medical monitoring during a daratumumab infusion

## Life-Threatening Conditions

Disease progression should not be recorded as an adverse event or serious adverse event term; instead, signs and symptoms of clinical sequelae resulting from disease progression/lack of efficacy will be reported if they fulfill the serious adverse event definition.

## 9.2 Procedures for Reporting Serious Adverse Events

### 9.2.1 Janssen SOP for Reporting Serious Adverse Events

As the sponsor of the study, the PI shall be solely responsible for complying, within the required timelines, any safety reporting obligation to competent Health Authorities, IRB/ECs and any participating (co or sub) investigators, as defined in applicable laws and regulations. For the purposes of this section, safety data includes adverse events, product quality complaints (PQCs), and special situations including pregnancies.

The PI will provide safety information to Janssen Scientific Affairs, LLC on adverse events, special situations including pregnancies and product quality complaints as defined within this section.

#### 9.2.1.1 Management of Safety Data

This Study has been designated as an interventional study. As such, all adverse events for Janssen Medicinal Products regardless of causality and special situations and product quality complaints with or without an adverse event as described in this Exhibit will be reported from the time a patient has signed and dated an Informed Consent Form (ICF) until completion of the patient's last study-related procedure (which may include contact for follow-up safety). Serious adverse events will be reported for 30 days after the last dose of study drug.

#### 9.2.1.2 Definitions Adverse Events of Special Interest

Adverse events of special interest are events that Janssen Scientific Affairs, LLC is actively monitoring as a result of a previously identified signal (even if non-serious). These adverse events are:

- Infusion reactions:  $\geq$  grade 3
- Infections:  $\geq$  grade 4
- Cytopenias:  $\geq$  grade 4
- Tumor lysis syndrome
- HBV Reactivation
- Other malignancies
- Intravascular hemolysis – all grades

Any Adverse Event of Special Interest that is to be reported to Janssen should be recorded on a Serious Adverse Event Report Form and be reported to the Janssen **within 24 hours of knowledge of the event.**

## Individual Case Safety Report (ICSR)

An ICSR is applicable when submitting information regarding an SAE, AE of special interest, Product Quality Complaint (PQC), or a Special Reporting Situations. A valid ICSR must contain the four minimum criteria required to meet regulatory reporting requirements.

- an identifiable patient (but not disclosing personal information such as the patient's name, initials or address)
- an identifiable reporter (investigational site)
- a Janssen medicinal product
- an adverse event, outcome, or certain special situations

The minimum information required is:

- suspected Janssen medicinal product (doses, indication)
- date of therapy (start and end date, if available)
- batch or lot number, if available
- patient details (patient ID and country)
- gender
- age at AE onset
- reporter ID
- adverse event detail (AE verbatim in English), onset date, relatedness, causality, action taken, outcome, (if available)
- Janssen protocol ID

